3.2 Exclusion Criteria

- 3.21 Prior treatment with regorafenib, cetuximab or panitumumab.
- 3.22 Major surgical procedure, open biopsy, or significant traumatic injury ≤ 28 days prior to randomization.
- 3.23 Congestive heart failure > New York Heart Association (NYHA) class 2.

NOTE: Class 3 is defined as marked limitation in activity due to symptoms, even during less-than-ordinary activity, e.g., walking short distances (20-100m). They are comfortable at rest. Class 4 is defined as patients with severe limitations. Experiences symptoms even while at rest. Mostly bed bound.

- 3.24 Unstable angina (angina symptoms at rest), new-onset angina (begun \leq 3 months prior to randomization) or myocardial infarction \leq 6 months prior to randomization.
- 3.25 Cardiac arrhythmias requiring anti-arrhythmic therapy. Note: Pacemakers, beta blockers or digoxin are permitted.
- 3.26 Uncontrolled hypertension. (Systolic blood pressure $>$ 140 mmHg or diastolic pressure $>$ 90 mmHg despite optimal medical management).
- 3.27 History of or current pheochromocytoma.
- 3.28 Arterial or venous thrombotic or embolic events such as cerebrovascular accident (including transient ischemic attacks), deep vein thrombosis or pulmonary embolism \leq 6 months prior to randomization.
- 3.29a Ongoing infection $>$ grade 2 NCI-CTCAE v5.0.
- 3.29b Known history of chronic hepatitis B or C.
- 3.29c Patients with seizure disorder requiring medication.
- 3.29d Symptomatic metastatic brain or meningeal tumors unless the patient is $>$ 6 months from definitive therapy, has a negative imaging study within 4 weeks of randomization and is clinically stable with respect to the tumor at the time of randomization. Note: Patient must not be undergoing acute steroid therapy or taper (chronic steroid therapy is acceptable provided that the dose is stable for one month prior to and following screening radiographic studies).
- 3.29e History of organ allograft (including corneal transplant).
- 3.29f Evidence or history of bleeding diathesis or any hemorrhage or bleeding event $>$ CTCAE v5.0 grade 3 \leq 4 weeks prior to randomization.
- 3.29g Non-healing wound, ulcer, or bone fracture.
- 3.29h Substance abuse, medical, psychological or social conditions that may interfere with the patient's participation in the study or evaluation of the study results.
- 3.29i MSI-H patients who have not received prior PD-1 mAb therapy.
- 3.29j Concurrent anti-cancer therapy \leq 3 weeks from randomization (chemotherapy, radiation therapy, surgery, immunotherapy, biologic therapy, or tumor embolization).
- 3.29k Known hypersensitivity to any of the study drugs, study drug classes, or excipients in the formulation.
- 3.29l Interstitial lung disease with ongoing signs and symptoms at the time of informed consent.

3.29m History of known persistent proteinuria of CTCAE v5.0 Grade 3 or higher (≥ 3.5 g/24 hrs).

3.29n Any malabsorption condition.

3.29o Unresolved toxicity greater than CTCAE v5.0 Grade 1 attributed to any prior therapy/procedure excluding alopecia and oxaliplatin induced neurotoxicity \leq Grade 2.

3.29p Albumin levels <2.5 g/dl.

3.29q Any of the following because this study involves an agent that has known genotoxic, mutagenic and teratogenic effects:

- Pregnant women
- Nursing women
- Men or women of childbearing potential who are unwilling to employ adequate contraception

NOTE: Men and women of childbearing potential must agree to use adequate contraception beginning at the signing of the ICF until at least 3 months after the last dose of study drug. The definition of adequate contraception will be based on the judgment of the principal investigator or a designated associate.

3.29r Co-morbid systemic illnesses or other severe concurrent disease which, in the judgment of the treating physician, would make the patient inappropriate for entry into this study or interfere significantly with the proper assessment of safety and toxicity of the prescribed regimens.

3.29s Known history of human immunodeficiency virus (HIV) infection or active hepatitis B or C infection requiring treatment with antiviral therapy.

3.29t Receiving any other investigational agent which would be considered as a treatment for the primary neoplasm.

3.29u Previous or concurrent cancer that is distinct in primary site or histology from colorectal cancer \leq 3 years prior to randomization EXCEPT for cervical cancer in-situ, treated ductal carcinoma in situ of the breast, curatively treated nonmelanoma skin carcinoma, noninvasive aerodigestive neoplasms, or superficial bladder tumor [Ta (Non-invasive tumor), Tis (Carcinoma in situ) and T1 (Tumor invades lamina propria)]. Note: All cancer treatments for cancers that were distinct in a primary site other than colorectal must be completed at least 3years prior to randomization (i.e., signature date of the informed consent form).

3.29v Pleural effusion or ascites that causes respiratory compromise (\geq CTCAE v5.0 Grade 2 dyspnea).

3.29w Any condition which, in the treating physician's opinion, makes the subject unsuitable for trial participation.

4.0 Test Schedule

4.1 Treatment with regorafenib

NOTE: Subjects should follow this test table while taking regorafenib regardless of treatment arm.

Tests and procedures	≤7 days prior to randomization	Active Monitoring Phase										End of All Treatment (within 30 days after last dose)	
		Cycle 1				Cycle 2				Prior to dosing each cycle beginning cycle 3+ (+/- 7 days)	Prior to dosing at restaging (C3 and every other cycle after) until progression (+/- 7 days)	End of Initial Treatment Mandatory Sequential Registration (if regorafenib is initial treatment) ¹²	
		Week 1 (Day 1)	Week 2 (Day 8)	Week 3 (Day 15)	Week 4 (Day 22)	Week 1 (Day 1)	Week 2 (Day 8)	Week 3 (Day 15)	Week 4 (Day 22)				
History and exam, weight, ECOG PS, blood pressure	X	X ⁷	X	X	X	X	X	X	X	X		X	X
Height	X												
Adverse event assessment	X				X				X	X		X	X
Hematology ⁵ CBC/ differential, ANC, INR/PTT ¹³	X	X ⁹				X				X			
Chemistry ⁵ SGOT (AST), alk phos, T. bili, serum creatinine, calcium, glucose, Na, K, SGPT (ALT), Mg	X	X ⁹		X		X		X		X			
Albumin ⁵	X	X ⁹			X				X				
Tumor Blood Bio-Markers (CEA)	X				X					X			
Tumor measurement ¹ (CT scan of chest, abdomen and pelvis), CT	X									X			X ⁶

component of a PET/CT, (MRI if CT is not feasible)												
ECG ⁴	X											
Serum pregnancy test ²	X	X ⁹										
Mandatory blood sample-plasma ^{10,R}		X				X						
STC1 biomarker blood collection ^R		X		X								
Mandatory tissue sample-archival tumor paraffin(see Section 17.0) ^{8, R}		X										
Patient Medication Diary (Appendix I) ³		X	X	X	X	X	X	X	X		X	X
Optional Blood sample -cfDNA Guardant 360 ^{10, 11, R}												X

1. CT scans preferred (MRI if CT is not feasible), CT component of a PET/CT, of the chest, abdomen and pelvis. Use same imaging throughout the study. Tumor measurements at baseline (≤ 28 days prior to randomization) and every 8 weeks beginning on cycle 3 day 1 prior to treatment until progression.
2. For women of childbearing potential only.
3. The diary must begin the day the patient starts taking the medication and must be completed per protocol and returned to the treating institution during each scheduled visit.
4. Performed at screening and then as needed.
5. Hematology and chemistry tests to be done prior to each cycle.
6. If patient goes off study during Cycle 1 and last CT scan was done > 28 days prior, the CT scan must be done.
7. If baseline history, exam, weight, ECOG PS, and blood pressure were performed ≤ 3 days of C1D1, they do not need to be repeated for C1D1.
8. Receipt of archival tumor tissue is not required for study randomization and initiation of therapy. However, it is mandatory to receive the required tissue ≤ 90 days from randomization. See section 17.0.
9. If screening tests occur ≤ 7 days prior to C1D1, they do not have to be repeated prior to dosing.
10. Kits are required for this collection. Refer to Section 14.0.

11. Patients have the option to complete cfDNA testing at study completion and will be allowed to register with protocol ACCRU-GI-1611. Site will access results through the Guardant Health portal: [REDACTED]. Sites will be notified by Guardant Health via email when results are available in the portal. Refer to Section 13.7. See detailed instructions on the ACCRU website under Manuals and Forms.
12. At the time of disease progression or intolerance from initial treatment, patients will be re-registered (See 6.3) to Sequential Treatment Phase. Tests should be completed after re-registration and prior to dosing of sequential treatment. Patients will then move to the cetuximab or panitumumab ± irinotecan test table (4.2).
13. If the INR/PTT is normal at screening (and subject is not on warfarin) this test will not need to be repeated unless indicated per investigator assessment. If a subject is on warfarin with stable INR/PT at baseline, the INR/PT should be assessed on Day 5 (+/- 3 days). If value is above the therapeutic range, the dose should be modified and the assessment should be repeated weekly until it is stable.

R Research funded.

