1.5 Regorafenib-related adverse events

In the CORRECT study, the common grade 3 or higher adverse events related to regorafenib were hand- foot-skin reaction (16.6%), fatigue (9.6%), hypertension (7.2%), diarrhea (7.2%), and rash/exfoliation (5.8%). Drug-related adverse events led to discontinuation of treatment in 8.2% in the regorafenib group and 1.2% in the placebo group¹⁹. It has been reported that adverse events, primarily hand- -foot-skin-reaction, occurred the most frequently in the first course, and the incidence decreased thereafter due to appropriate dose reduction²¹.

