7.0 Protocol Treatment

Drugs will be administered in accordance with the information on the respective package inserts. Treatment will be given according to the schedule specified in the protocol. The terms “delay,” “modification,” and “omission” are defined as follows:

Delay: A delay indicates dose was postponed or not received when expected.

Modification: Indicates a change in dose level during the current cycle. However, if a modification was issued after the last dose was received in the current cycle, the modification should be reported on the subsequent cycle.

Omission: Indicates a dose was skipped and not made up, or that the drug was discontinued.

Arm A, treatment with regorafenib followed by anti-EGFR therapy (\pm irinotecan).

Arm B, treatment with anti-EGFR therapy (\pm irinotecan) followed by regorafenib.

Treatment on regorafenib will be continued in accordance with Section 7.11 “Planned treatment with regorafenib” until any of the “Criteria for discontinuing treatment with regorafenib” (Section 8.34) is met.

Treatment on Anti-EGFR therapy (\pm irinotecan) will be continued in accordance with Section 8.4, “Combination therapy of Anti-EGFR therapy (cetuximab (Cmab) **OR** panitumumab (Pmab) and irinotecan” until any of the “Criteria for discontinuing treatment including Cmab or Pmab” (Section 8.44) is met.

Patients assigned to Anti-EGFR therapy will receive either cetuximab or panitumumab per treating physician discretion and will be dosed per prescribing guidelines. Patients cannot switch between cetuximab and panitumumab during the course of the study. The use of irinotecan is per treating physician discretion and will be dosed per prescribing guidelines. If treating physician chooses to add irinotecan, irinotecan must be included in treatment starting at cycle 1.

7.1 Treatment Schedule - Use actual weight or estimated dry weight if fluid retention

Agent	Dose	Route	Frequency	ReRx
Regorafenib	80mg daily (Starting dose) See table 7.11	PO	Daily for Days 1-21 of 28 day cycle	Every 28 days
Cetuximab*	500mg/m ²	IV	Days 1, 15	Every 28 days
Panitumumab*	6mg/kg	IV	Days 1, 15	Every 28 Days
Irinotecan	180mg/m ²	IV	Days 1, 15	Every 28 days

* Patients assigned to Anti-EGFR therapy will receive **EITHER** cetuximab **OR** panitumumab, not both

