***starting dose level**

1 Dose escalation/reduction should follow section 8.1

Cycle 2 and beyond:

Week	Dose
1	Remain at highest tolerated dose from Cycle 1 (up to 160 mg)
2	
3	
4	Off

Regorafenib tablets should be taken once a day with approximately 8 fluid ounces (240 mL) of water after a low-fat (<30% fat) meal. Regorafenib should be taken with a meal at the same time every day. Some examples of low fat meals are:

- Two slices of white toast with 1 tablespoon of low-fat margarine and 1 tablespoon of jelly and 8 ounces (240 mL) of skim milk (approximately 319 calories and 8.2 g of fat).
- One cup of cereal (i.e. Special K), 8 ounces (240 mL) of skim milk, one piece of toast with jam (no butter or marmalade), apple juice, and one cup of coffee or tea (2 g fat, 17 g protein, 93 g of carbohydrate, 520 calories).

If vomiting occurs shortly after regorafenib are swallowed, the dose should only be replaced if all of the intact tablets can be seen and counted. Should any patient enrolled on the study miss a scheduled dose for whatever reason (e.g. as a result of forgetting to take the tablets or vomiting), the patient will be allowed to take the scheduled dose up to a maximum of 2 hours after that scheduled dose time. If greater than 2 hours after the scheduled dose time, the missed dose is not to be taken and the patient should take their allotted dose at the next scheduled time.

7.2 Planned treatment with Anti-EGFR therapy (cetuximab (Cmab) or panitumumab (Pmab)) and irinotecan. Refer to 8.4 for treatment initiation requirements.\

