8.0 Dosage Modification Based on Adverse Events

Strictly follow the modifications in the following tables for the first **two** cycles, until individual treatment tolerance can be ascertained. Thereafter, these modifications should be regarded as guidelines to produce mild-to-moderate, but not debilitating, side effects. If multiple adverse events are seen, administer dose based on greatest reduction required for any single adverse event observed. Reductions or increases apply to treatment given in the preceding cycle and are based on adverse events observed since the prior dose.

ALERT: *ADR reporting may be required for some adverse events (See Section 10)*

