8.1 Regorafenib Dose Escalation/Reduction

Dose level	If No SDRT	If + SDRT**
80 mg*	Proceed to next dose level	-
120 mg	Proceed to next dose level	Decrease to 80 mg
160 mg	-	Decrease to 120 mg

*starting dose level

**SDRT = Significant Drug Related Toxicities

- 8.11 After week 8, if toxicities have resolved to ≤ Grade 0-1, re-escalation is allowed 40 mg at a time every 4 weeks to a maximum of 160 mg and at the discretion of the treating physician.
- 8.12 Patients with dose reductions below 80 mg should go off treatment and go to event monitoring.
- 8.13 Any patients with toxicities requiring >4 week delay should go off treatment and then to event monitoring.

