8.2 Regorafenib Dose Modifications

8.21 Regorafenib may be dose reduced per the table 8.21 in case of intolerable toxicity such as weight loss, fatigue, rash or anorexia.

Table 8.21 Recommended dose modification for toxicities except hand-foot-skin reaction, hypertension and ALT/AST/bilirubin			
NCI-CTCAE v5.0^a	Dose Delay	Dose Modification ^b	Dose for Subsequent Cycles
Grade 0-2	Treat on time	No change	
Grade 3	Delay until \leq Grade 2 ^c	Reduce by 1 dose level	If toxicity remains $<$ Grade 2, dose re-escalation can be considered at the discretion of the treating physician. If dose is re-escalated and toxicity (\geq Grade 3) recurs, institute permanent dose reduction.
Grade 4	Delay until \leq Grade 2 ^c	Reduce by 1 dose level. Permanent discontinuation can be considered at treating physician's discretion.	

^a NCI-CTCAE = National Cancer Institute - Common Terminology Criteria for Adverse Events, version 5.0
^b Excludes alopecia, non-refractory nausea/vomiting, lymphocyte count decreased, non-refractory hypersensitivity and nonclinical and asymptomatic laboratory abnormalities.
^c If no recovery after a 4 week delay*, treatment should be permanently discontinued unless subject is deriving clinical benefit.
* Modify according to study specific cycle length

If greater than 2 dose level reductions are required, regorafenib will be discontinued and the rest of the study follow up may be continued. The following tables outline dose adjustments for toxicities related to regorafenib except hand-foot skin reaction, hypertension and liver function test abnormalities.

The table above outlines dose adjustments for hematologic and non-hematologic toxicities related to regorafenib except PPES and hypertension. In addition to these recommended dose modifications, subjects who develop diarrhea, mucositis, anorexia or other events predisposing to fluid loss or inadequate fluid intake should be carefully monitored and rehydrated as clinically necessary. This is in order to minimize the risk of postural hypotension and renal failure.

8.22 Regorafenib may be dose reduced per Table 8.22b in case of Palmar-plantar erythrodysesthesia using Table 8.22a for grading guidelines.

Table 8.22a: Grading for Palmar-plantar erythrodysesthesia syndrome			
	Grade 1	Grade 2	Grade 3

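### Table 4.1 schedules no blood count between the first and last regorafenib dose of cycle 1 or cycle 2, so transient cytopenias can be missed and are looked for half as often in Arm A as in Arm B during initial treatment

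*Combined protocol and SAP*

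**What the plan says.** **Test schedule on regorafenib.** In Table 4.1 the hematology row (CBC with differential, ANC, INR/PTT) is marked at screening, C1D1, C2D1 and before each cycle from cycle 3. It is blank on Days 8, 15 and 22 of cycles 1 and 2. Footnote 5 agrees: "Hematology and chemistry tests to be done prior to each cycle". Under footnote 9, if screening tests were done within 7 days before C1D1, "they do not have to be repeated prior to dosing". The chemistry row has additional draws on Day 15 of both cycles, in line with the two-weekly liver tests that section 8.24 requires.

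**Dosing.** Section 7.1 gives regorafenib "Daily for Days 1-21 of 28 day cycle". Section 7.11 raises the cycle 1 dose weekly: 80 mg, 120 mg, then 160 mg from Day 15.

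**Rules that depend on a count.** Section 8.5 calls for treatment to be interrupted, for up to 4 weeks, at grade 3 or 4 neutropenia, leukopenia or thrombocytopenia. It names no particular drug. Section 8.0 makes the modification tables strict for the first two cycles, "until individual treatment tolerance can be ascertained". Section 15.17 lists neutropenia and thrombocytopenia among regorafenib events above 10%, without grade. Section 15.196 tells staff to monitor the CBC but gives no days.

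**The other regimen.** Table 4.2 (anti-EGFR ± irinotecan) marks hematology on Day 1 and Day 15 of cycles 1 and 2, with a Day 15 column for later cycles.

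**The concern.** Section 8.5 acts on a laboratory grade, yet in the two cycles that section 8.0 treats most strictly the regorafenib schedule provides no count while the patient is taking tablets. Each post-dose count comes after a week off drug, when a fall in neutrophils or platelets may already have recovered. A patient with such a fall and no symptoms would keep taking tablets through Day 21, and in cycle 1 might step up to 160 mg, with no scheduled test to show it.

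The second issue is comparability. Goal 2.24 and section 16.12 compare adverse events between arms, and 16.12 does so separately for initial treatment, sequential treatment and the whole period. In initial treatment Arm A follows Table 4.1 and Arm B follows Table 4.2. A laboratory cytopenia can be recorded only if blood is drawn, so a difference between arms in these events would partly reflect how often each arm was tested.

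**Working it through.** The plan states no figure to reproduce. The check compares test days with dosing days, numbering study days from C1D1 = Day 1 with 28-day cycles.

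**Inputs.** Dosing on Days 1-21 of 28 (7.1). Hematology and chemistry days (Tables 4.1 and 4.2). Screening count allowed up to 7 days before C1D1 (4.1, footnote 9). Administrative window of ±3 days on Day 1 (7.3). Window of ±7 days on pre-cycle tests from cycle 3 (4.1). 60 right-sided patients (16.22).

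**1. Counts on drug as scheduled.**
- Dosing days: 1-21 and 29-49.
- Scheduled counts: Day 1 (pre-dose, or screening), Day 29 (pre-dose), then Day 57 before cycle 3.
- Counts between the first and last dose of a cycle: 0 in cycle 1 and 0 in cycle 2.
- Last cycle 1 tablet to the C2D1 count: 29 − 21 = 8 days. Last cycle 2 tablet to the C3D1 count: 57 − 49 = 8 days.

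**2. Whether the visit windows change this.**
- C2D1 moved forward 3 days falls on Day 26, still off drug.
- From cycle 3, a pre-cycle test 7 days early falls on Day 22 of the preceding cycle (29 − 7 = 22), the first off day. It too is off drug.

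**3. Intervals between scheduled counts.**

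| | As written | With CBC on Day 15 |
|---|---|---|
| C1D1 to next count | 29 − 1 = 28 days | 15 − 1 = 14 days |
| Screening count (footnote 9) to next count | 28 + 7 = 35 days | 14 + 7 = 21 days |
| C2D1 to next count | 57 − 29 = 28 days | 43 − 29 = 14 days |
| On-drug counts, cycles 1-2 | 0 | 2 |

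**4. Arms in initial treatment, cycles 1-2.**
- Arm A (Table 4.1): C1D1 and C2D1, 2 counts, 28 days apart.
- Arm B (Table 4.2): C1D1, C1D15, C2D1 and C2D15, 4 counts, 14 days apart.
- With the fix, Arm A also has 4, on the same days. In sequential treatment the arms exchange tables, so the imbalance runs the other way and the same edit removes it for cycles 1-2.

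**5. The most a Day 15 result can change.** It can affect the doses on Days 15-21, which are 7 of the 21 dosing days in a cycle.

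**6. Cost.** 2 tubes × 60 patients = 120 tubes at most, reached only if every right-sided patient gets to Day 15 of regorafenib cycle 2.

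**The case against.** The strongest defence is that the schedule is proportionate. Regorafenib carries a boxed liver warning and gets two-weekly liver tests. Irinotecan carries a boxed myelosuppression warning, and its table has Day 15 counts. Section 1.5 says that in the cited phase III trial "the common grade 3 or higher adverse events related to regorafenib were" hand-foot skin reaction, fatigue, hypertension, diarrhea and rash; no cytopenia is named. Nothing in the plan requires a mid-cycle CBC on regorafenib. This stands, and it is why the point has low priority.

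The patients at issue are also few in kind. A cytopenia that persists to C2D1 is caught there. One with symptoms can prompt a CBC at a weekly exam. For the rest, Table 8.21 footnote b exempts "nonclinical and asymptomatic laboratory abnormalities", and section 8.5 allows restart at the same dose after recovery. This stands only in part. The footnote is attached to the dose-modification column, not to dose delay. Section 8.5 has no such exemption and requires recovery to grade 1 or less before restart.

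Four stronger readings are tempting but not supported:
- *The section 8.5 rule has nothing to act on.* What is missing is a scheduled on-drug count. Section 8.5 asks for close follow-up, 15.196 for CBC monitoring, and the C2D1 count can itself trigger an interruption or delay.
- *The share of the dose taken after Day 15 measures the risk.* It measures tablets. The documents give no nadir, recovery time or grade 3/4 rate to turn it into risk.
- *Footnote 5 is an error because it omits Day 15 chemistry.* Footnote 4 of Table 4.2 has the same wording and sits beside Day 15 draws, so it can be read as a minimum.
- *A missed count means a wrong step to 160 mg.* Section 8.1 ties escalation to "SDRT = Significant Drug Related Toxicities" and does not say that a laboratory-only cytopenia qualifies. That remains the physician's judgement.

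**Conclusion.** The point holds for scheduled counts. In cycles 1 and 2 on regorafenib none falls between the first and last dose of a cycle, and the longest scheduled interval is 28 days (35 from a footnote 9 screening count). Two consequences follow. An asymptomatic grade 3/4 neutropenia, leukopenia or thrombocytopenia that recovers in the off-week will not trigger section 8.5 unless an unscheduled CBC is drawn. And in initial treatment Arm B is counted twice as often as Arm A over these cycles, so laboratory cytopenias are detected unequally in the adverse event comparison.

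The first consequence assumes that some such cytopenias arise and recover within the cycle; the documents neither show nor exclude this. The safety gain is therefore modest and unquantified. The unequal detection follows from the schedules alone, but its effect on observed rates cannot be sized either. Overall survival is not affected. A reader might infer that the trial is unsafe without a mid-cycle CBC; the documents do not support that. This is a cheap improvement of low priority.

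**What to change.** In Table 4.1, mark CBC/differential at the existing Day 15 chemistry draws of cycles 1 and 2, with a footnote such as: 'CBC/differential only (not INR/PTT) is also drawn on Day 15 of cycles 1 and 2.' Naming the CBC matters because the hematology row also contains INR/PTT, and marking the whole row would add coagulation tests for patients not exempt under footnote 13.

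The cost is one table and footnote edit and one extra tube at two existing draws, with no new visit. The downside is a few more asymptomatic findings to manage. The C1D15 result is useful for the step to 160 mg only if it is back before that day's tablets.

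The limits should be stated openly. C1D15 precedes the first 160 mg tablet and so does not cover week 3 of cycle 1. From cycle 3, Table 4.1 has no Day 15 draw to attach a count to, so later cycles keep the present pattern and the difference from Table 4.2 remains there. The adverse event report should say so when laboratory cytopenias are compared between arms.
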